### 1. Abstract

Adolescents and young adults less than 25 years of age continue to have the highest rates of sexually transmitted infections [STIs] in the United States. While public health control programs have shown some success the disparities for this population remain. For this reason additional supports to increase engagement in care and reduction in acquisition of STIs as a part of establishing a healthy sexuality are needed. STI prevention work with adolescents has primarily targeted individual level factors and fails to address higher level factors such as peer, media, and relationship influences that may influence sexual decision-making and behavior. Partner notification and treatment is a key strategy for disease control within the population to improve the health and well-being of the individuals affected by the disease process and has previously been explored among adults for STI/HIV prevention work but has yet to be explored in adolescents and young adults. In our prior research, we demonstrated that adolescent girls with complicated sexually transmitted infections are highly likely to notify their partners for treatment (88-92%), but that only those who experience brief behavioral interventions are 3 times more likely to be successful in arranging for partner treatment than girls receiving standard of care. There has been a failure to use our knowledge about the structure and function of romantic relationships occurring during critical developmental learning periods, to engage youth for individual and dyadic behavior change. Partner interventions for STI prevention have significant promise for harnessing the power of relationship dynamics to enhance sexual decision-making, communication, and subsequent health behaviors. In the EXPERIENCE study, we propose to pilot an intervention designed to change STI outcomes by understanding partners and the learning environment related to sex. If successful, this pilot will support adoption of an alternative cost conscious, but effective strategy for engaging young men involved in sexual relationships affected by an STI diagnosis for both individual and relationship behavior change. Proving that heterosexual adolescents and young adults can consistently and safely engage their partners in a supportive outpatient setting that integrates treatment with evidence-based STI/HIV prevention interventions delivered by gender matched professional dyads.

During this COVID-19 pandemic, urban centers have been hard hit, but there has been little discussion regarding the impacts of sexual behavior and relationship interactions on the spread of COVID-19 within the community. The Women's BioHealth cohort presents a vulnerable group of adolescent and young adults (AYA) who may be able to provide insights on how COVID-19 stay at home orders have impacted sexual behaviors and overall risk for STIs. COVID-19 stay at home orders may complicate the social situations for some AYA in the greater Baltimore Metropolitan Area given the known disparities in health, poverty, housing, and violence. We would like to conduct follow-up outreach calls to the Tech2Check participants to include questions about impacts of COVID-19 stay at home orders on sexual risk-taking behaviors, access and unmet need for sexual and reproductive health (SRH) services. We include assessments of social support, perceived safety, and resources to evaluate the impact of those factors on SRH risks. We also determine need for re-engagement in care and willingness/ability to use telemedicine services to fulfill unmet health needs.

## 2. Objectives

1. To demonstrate the feasibility of the dyadic intervention for young urban dyads with a recent STI diagnosis as evidenced by recruitment and short-term retention [6 weeks].
2. To demonstrate acceptability of a dyadic intervention for STI/HIV prevention for urban young dyads with a recent STI diagnosis as evidenced by appointment attendance, visit completion, and satisfaction by those who complete the intervention.
3. To demonstrate the preliminary effectiveness of the intervention for increasing mutual sexual negotiation self-efficacy and self-reported communal coping at the end of the intervention visit and condom consistency at 6 weeks compared with dyads who receive *individual interventions* in a primary care setting to better operationalize the notion of transformational motivation in AYA dyads in the context of sexual relationships.
4. To improve our understanding of urban adolescent and young adult relationships in which a STI diagnosis has occurred and the extent to which partner dynamics and social context influence sexual health among urban partner-dyads affected by a STI diagnosis using in-depth interviews.

The focus of this pilot will be on completion of EXPERIENCE study visits, delivery of the intervention, patient satisfaction with the experience, and learning more about relationships and sexual health among young dyads that will inform any future iterations of the dyadic intervention.

### **To evaluate the impact of the COVID-19 stay-at home orders on TECH-N participants' SRH behaviors and risk for STI.**

**Hypothesis 1:** AYA with a greater number of psychosocial risk factors across housing, food insecurity, income, and social support will have greater engagement in sexual risk-taking behaviors (e.g. non-condom use, non-use of contraception) during the COVID-19 stay at home order.

**Hypothesis 2:** AYA with reduced SRH risk-taking behaviors during the COVID-19 stay at home orders are more likely to engage in increased SRH risk-taking behaviors once the order has been lifted.

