### **COVID-19 Survey**

We will conduct outreach regarding COVID-19 via phone. Questions will include basic information about living conditions, sexual behavior, relationship status, and SRH behaviors and healthcare needs since the stay-at-home order [March 16, 2019 (school closings)] through the present. We will interview individuals at baseline and three months from their designated call to determine if there is any change in behavior or circumstance [attached].

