### **Quality Control**

**1. Treatment Fidelity:** Drs. [name] and [name] [with technical assistance [TA] for specific interventions] will train and supervise research staff to ensure protocol execution with dyads.

**2. Recruitment Screener:** Includes collection of basic demographic data and the outcome of recruitment effort so that we can keep an accurate account of referral patients who are ineligible and/or refuse to participate in the intervention. We include a standard question about (intimate partner violence) IPV in the screener to determine if this is a reason for refusal and/or influence the communication/behavior in the relationship over time. Participants who screen positively, will be provided with information and resources about IPV in the individual visit and referrals placed to the primary health provider for additional services.

**3. Surveys:** We have developed a survey to collect sexual and reproductive health history, perceived barriers to treatment, and self-efficacy data to be administered online during the study visit. This interview will be modified for this study, but will include: demographics, reproductive and sexual history (# partners, partner status (main versus casual), relationship status, coital frequency, prior STIs, condom use consistency, contraceptive use preferences for partner notification (e.g. female partner notification, case worker notification, email, text message), emotional response to diagnosis, access to medical care, access to technology (phone, internet, text), social provisions scale, and the short-form survey instrument (SF-12) as a measure of health-related quality of life, Fertility Knowledge and Awareness Scale, clinical symptoms, sensation seeking scale, relationship qualities scale and intimate disclosure scales to measure relationship quality and dyad communication, childbearing motivation and communal coping. We will also query patients at the end of the intervention to determine their level of confidence for negotiating with their partner and their satisfaction with the experience. It is important to test these measures with participants and the timing of completion.

Participants will be contacted in 6-8 weeks for a brief (~30 min) telephone (or in-person) follow-up interview to assess sexual risk-taking behaviors, relationship status, social support, and satisfaction with the intervention experience.

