#### COVID-19 Outreach Study

Descriptive and bivariate analyses will be performed to determine the general impact of COVID-19 risk on AYA in the sample and to evaluate the covariates such as change in living situation, cohabitation, stress, access to SRH services and COVID-fears on SRH behaviors.

Bivariate analyses generating  $p \leq 0.1$  will be evaluated using logistic regression models, accounting for potential confounders or effect modifiers.

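### The COVID-19 aim is the impact of the stay-at-home order, but the planned analysis names no pre-order value, so Hypothesis 1 can show only an association during the order and 'reduced' in Hypothesis 2 has no reference level

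*Combined protocol and SAP*

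**What the plan says.** - **Aim** (section 2, COVID-19 objective): "To evaluate the impact of the COVID-19 stay-at home orders" on the SRH behaviours and STI risk of TECH-N participants.
- **Hypothesis 1** (same place): young people with more psychosocial risk factors "will have greater engagement in sexual risk-taking behaviors (e.g. non-condom use, non-use of contraception) during the COVID-19 stay at home order". This compares people within the order period.
- **Hypothesis 2** (same place): the exposed group is "AYA with reduced SRH risk-taking behaviors during the COVID-19 stay at home orders". No reference level is given.
- **Data** (section 4, COVID-19 Survey): questions cover "SRH behaviors and healthcare needs since the stay-at-home order [March 16, 2019 (school closings)] through the present". Calls are made at a first contact, labelled baseline, and three months later. The questionnaire is marked as attached and is not in the text reviewed.
- **Analysis** (section 7, COVID-19 Outreach Study): "Descriptive and bivariate analyses will be performed to determine the general impact of COVID-19 risk on AYA in the sample", followed by logistic regression for bivariate results with p≤0.1, allowing for potential confounders or effect modifiers that are not named. Among the example covariates, only living situation is expressed as a change.
- **Who is called** (section 1): the plan is to "conduct follow-up outreach calls to the Tech2Check participants", so respondents already belong to a cohort. No section plans a link to their earlier data.

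**The concern.** Impact means a difference from what behaviour would have been without the order. Both calls fall after the order began, so the call labelled baseline is not a pre-order baseline, and change between calls is not change from before the order.

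The exposures in Hypothesis 1 (housing, food insecurity, income, social support) can long predate the order. If people with more hardship already had higher-risk behaviour, Hypothesis 1 would be met even if the order changed nothing. A positive result would then fit both an effect of the order and a continuing difference, and the planned analysis could not separate them. Hypothesis 2 has the same gap in its exposure definition: without a stated reference level, respondents cannot be classified reproducibly as having reduced their risk behaviour.

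**Working it through.** **No figure to reproduce.** The documents give no sample size, effect size, event rate or correlation for this add-on. Everything below rests on assumed inputs.

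**1. What each analysis estimates.** Let x be hardship, P the behaviour before the order and D the behaviour during it, each with variance 1. Let a = corr(x,P), ρ = corr(P,D) and g = corr(x,D). The slopes on x are:
- during-order only: g
- adjusted for P: (g − aρ)/(1 − a²)
- within-person change D − P: g − a

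Take a = 0.3 and ρ = 0.6, and two models in which the order has no hardship-related effect:
- **Fading gap.** Hardship acts on D only through P, so g = 0.3 × 0.6 = 0.18. During-order slope 0.18; adjusted slope 0; change slope 0.18 − 0.30 = −0.12.
- **Constant gap.** g = 0.30. During-order slope 0.30; adjusted slope (0.30 − 0.18)/(1 − 0.09) = 0.12/0.91 = 0.13; change slope 0.

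The during-order slope is non-zero in both. Each pre-order analysis is correct under one model and biased under the other.

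For any g between 0.18 and 0.30 the adjusted slope is positive and the change slope negative. They share a sign only if the gap widens beyond 0.30 or shrinks below 0.18. That is the reason for requiring agreement.

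**2. Rejection rates.** 1,500 simulated studies per setting; D split at its median for the logistic models; change analysed on the continuous scale; p<0.05.

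| No-effect model | Analysis | N=100 | N=200 | N=300 |
|---|---|---|---|---|
| Fading gap | During-order only | 29% | 54% | 70% |
| Fading gap | Adjusted for P | 4–5% | 4–5% | 4–5% |
| Fading gap | Within-person change | 27% | 45% | 63% |
| Constant gap | During-order only | 66% | 93% | 99% |
| Constant gap | Adjusted for P | 18% | 37% | 51% |
| Constant gap | Within-person change | 5–7% | 5–7% | 5–7% |

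In the fading-gap model the median during-order odds ratio is about 1.35 per SD of hardship. Other correlations in that model move the during-order rate to 12–27% (a = 0.2, ρ = 0.5) or 61–98% (a = 0.4, ρ = 0.7) over the same sample sizes.

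**3. Coarse measurement.** If P is reduced to a binary variable, adjustment works less well: 6–13% in the fading-gap model and 33/61/80% in the constant-gap model.

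**4. The plan's own screen (p≤0.1).** Take two hardship groups with a stable difference and no effect of the order. At assumed rates of 40% and 60%, the odds ratio is (0.60/0.40)/(0.40/0.60) = 2.25, and the chance of passing the screen is 41%, 64% and 89% with 25, 50 and 100 per group. Over rates from 45/55% to 35/65% the chance runs from 17% to 99.7%. Comparing change between groups gives about 10–11%, the nominal rate.

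**The case against.** The strongest reply is that Hypothesis 1 is worded as an association during the order and the plan tests it as worded. On that reading, the rates above are detection of a real association and not false positives. This stands. The fault lies in placing that test under an impact aim. A reader might infer that long-standing differences will be read as effects of the order; the documents do not say how results will be interpreted, so that is a forecast.

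Three further points stand in part.
- The questionnaire is not shown and may contain before-and-since items. It cannot be said that no pre-order information is collected, only that the analysis text uses none.
- The covariate list is open and confounders are left general. Prior behaviour is unspecified, not excluded.
- A reader might infer that the pre-order data are already in hand, because the EXPERIENCE survey (section 4, Quality Control, item 3) records "coital frequency, prior STIs, condom use consistency". But the COVID-19 aim names TECH-N and the abstract names Tech2Check and Women's BioHealth, and the documents do not show what those cohorts recorded or when. Within EXPERIENCE, the later participants were enrolled virtually because of the pandemic, so their baseline is probably not pre-order.

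It is also tempting to conclude that adjusting for the pre-order value settles the matter. The table shows that it does so only if the gap fades.

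**Conclusion.** The aim, the survey window and the analysis text do not match. As written, the add-on can report associations during the order, but it cannot attribute them to the order, and Hypothesis 2 lacks a definition for its exposure.

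The direction of the problem follows whenever hardship and prior behaviour are positively correlated and behaviour persists. Its size is not known: the 29–70% and 66–99% depend on assumed sample sizes and correlations. Pre-order data would help in either model, since adjustment alone lowers 29/54/70% to about 5%, and 66/93/99% to 18/37/51%. No single analysis is right under both.

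Even within-person change is not a proven causal effect. There is no unexposed comparator, and ageing, relationship turnover and any study intervention since the earlier survey are mixed in.

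The point concerns only the COVID-19 telephone add-on. The feasibility and acceptability outcomes of the randomised pilot are not affected.

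**What to change.** In section 7, COVID-19 Outreach Study:
1. State whether the called cohort has surveys dated before the order. Where it does, link each respondent's last such survey to the call data. Confirm the order date, printed in the COVID-19 Survey section as March 16, 2019, because it decides which surveys count as pre-order.
2. For the impact question, report the hardship association (a) adjusted for the pre-order value of the same behaviour, kept as finely measured as possible, and (b) as within-person change. Claim a hardship-related effect of the order only if the two agree.
3. Define 'reduced' in Hypothesis 2 against that pre-order value.
4. Let respondents without a pre-order survey contribute only to the during-order association.
5. Describe (b) as change since before the order, not as a proven causal effect.
6. If no pre-order data exist for the called cohort, restate the aim in section 2 as associations during the order, and give Hypothesis 2 a reference level that the survey can supply.

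Cost: a record link, one more analysis and a smaller sample for the impact question. If step 6 applies, the cost is a change of wording and a narrower claim.

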## 3. Background

Our team has conducted prior research that serves as a backdrop for dyadic research with adolescent and young adults and a strategy to reach males for treatment and preventive services. Our Gender-Based Differences Study utilized secondary data analysis from the Adolescent Health Study, a population-based telephone survey study in which urban adolescents from a high STI-prevalent community were queried about their sexual experience, fertility-related knowledge, beliefs related to timing of childbearing, and risk assessment of future fertility problems. Regression analyses indicated that female adolescents were more likely than male adolescents to identify chlamydia and pelvic inflammatory disease as causes of fertility problems. The most disturbing finding was that 72% of adolescent girls perceived significant risk for future fertility problems and almost 60% thought they had little or no control over it. We surmised that additional health education and motivation would be needed to increase adolescent participation in asymptomatic STI screening programs and the greatest challenge would be how to involve male adolescents given that fewer male adolescents understand the link between female fertility and common STI-related conditions despite their high value for partner fertility.

The Young Women's Health study (was a randomized controlled trial (RCT) funded by the Robert Wood Johnson Foundation that tested the effectiveness of a brief video intervention grounded in the health belief model to improve self-care behaviors associated with PID. The study was conducted at

two institutions with clinic and emergency department sites in Baltimore, Maryland covering census tracts most affected by STIs. The major finding from this work was that it demonstrated that the group viewing the video intervention prior to discharge [which included the treatment tag line “.... if he loves you, he’ll do it right?”] was significantly more likely to engage in secondary prevention through partner notification for treatment compared to the standard of care control group. Although there were no differences in the rates of partner notification, girls in the intervention arm were 3 times more likely to facilitate partner treatment. This work suggests that one of the most powerful elements of intervention after an STI is partner engagement.

### **Male Sexual and Reproductive Health Needs**

[name] has conducted extensive research with young men demonstrating the impact of STIs on young men and has been intrinsically involved in 1) guiding diagnostic testing, screening, and prevention approaches for STIs 2) pushing the field by using internet ordered-self-testing and 3) evaluating new diagnostic tests for STIs to further improve public health outcomes for men. [name] conducted secondary analyses of data from the Adolescent Health study, a household study of urban adolescents 15-19 years in high STI prevalent communities in California, which demonstrated the high value of future fertility to youth across gender, but significant gender-based differences in STI knowledge as it related to infertility prevention. We identified the need at that time to involve male adolescents in STI prevention efforts given the high value they place on fertility preservation.

[figure not shown]
In a series of projects lead by our team, the evidence for investment in and guidance for male sexual and reproductive health (SRH) services has been established. As an example, an analysis of data from the National Survey on Family Growth demonstrated that adolescent males were significantly less likely than female youth to receive SRH counseling from their health providers. In a more recent cross-sectional study of 16-35 year old males, 346 participants' willingness to talk about 11 SRH topics with their healthcare provider and their preferred approach (provider- or self-initiated) was examined. Almost all participants (84%–98%) were willing to talk about all SRH topics and the top three were STI risk (98%); testicular cancer (98%); and HPV vaccine (97%). The majority preferred that the health provider initiated discussions, demonstrating the potential openness to clinic-based conversations by health providers as a proactive strategy for prevention with males experiencing STI exposure and/or diagnosis. An earlier analysis demonstrated that this work could be performed in clinical settings primarily geared towards women. This suggests that seeking care in a non-gendered adolescent-centered practice as employed in our design may be equally or more conducive male engagement. Finally, a sexual health curriculum for SRH was developed for use in a Baltimore youth employment and training program in 2008–2010 involving 197, mostly African American males aged 16–24 years. Ninety-eight participants received three one-hour curriculum sessions on consecutive days; 99 served as controls. In analyses adjusting for baseline characteristics, intervention participants 3 months later were more likely than control males to report increases in knowledge of STIs and health care use (odds ratio, 1.6 for each), frequency of condom use (1.8), use of lubricant with condoms (23.6), communication with a provider about STIs (12.3) and STD testing (16.6). We will use the specific experiences in implementation of a male SRH intervention to incorporate and effectively engage the male partner as a part of the STI treatment visit.

The Perceived Risks for Sexually Transmitted Diseases (PRSTD) Study showed the importance of measuring risk perception in a partner specific manner, a second cohort was recruited and followed prospectively for three years to determine 1) age-related patterns of sexual behavior and STD acquisition among adolescents and young adults, 2) how an adolescents' relative power in a sexual relationship affects condom behavior, 3) the accuracy of adolescents' partner-specific PRSTD, and the concordance of childbearing plans among adolescent heterosexual dyads. Data was collected from 392 sexually experienced 14 - 19 year old males and females who were seeking care at either the Baltimore City Health Department STD clinic or the Johns Hopkins Adolescent Medicine Clinic.

Most recent main sex partners of a random selection of participants at baseline were recruited into the study resulting in data on 132 adolescent heterosexual dyads. This dyadic data has led to significant contributions to the literature, leading to a greater understanding of the poor agreement between adolescents' perception of their partner having other sex partners and partner-reported behavior, such that adolescents who presume that they are in a mutually monogamous relationship often underestimate their own sexually transmitted disease risk. Findings from the second cohort motivated recruitment of a third prospective cohort, which collected daily electronic diaries to examine how changes in intimacy and perceived partner concurrency impact STD risk perception, sexual behaviors, and STD acquisition over time within adolescent dating relationships. Data from this cohort has shown significant variability in adolescents' STI-associated feelings, perceptions, and behaviors within their sexual relationships and that this variability predicts behavior. Further findings demonstrate that adolescent relationships last for a long duration despite concurrency within the relationship. It is on this premise that we further build our case for intervention designed to reduce and improve the quality of the relationship with this vulnerable population of youth.

